10.2. Sample Size Justification

Meta-analysis

As described above, a meta-analysis was executed to determine the safety Performance Goals for the proposed NAPA clinical study of the PulseRider using the R package ‘meta^a’ in a [R] environment, version 3.3-2. To obtain an overall proportion from studies reporting a single proportion, a random-effects model was chosen over a fixed-effect model to acknowledge the variations in study design. Additional characteristics of the methodology are:

- Inverse variance method used for weights
- DerSimonian-Laird method used to estimate τ^2
- Logit transformation
- Clopper-Pearson confidence interval for individual studies
- Continuity correction of 0.5 in studies with zero cell frequencies

Based on this meta-analysis, a rate of 9.9% rounded to 10% (95% CI: 5.9% - 16.1%) for death due to neurological causes or major ipsilateral stroke was calculated. A 5% margin of indifference for the primary safety endpoint is proposed, resulting in a PG of 15% for this endpoint. Based on the 1 year results of the ANSWER HDE Study, the anticipated rate for the primary safety endpoint is 7%. Results from a recently published meta-analysis [Fiorella 2017] of wide-neck bifurcation aneurysms indicate that the rate of complete occlusion at 1 year of wide-neck bifurcated aneurysms treated with conventional therapies is 46.3% (95% CI: 39.2% - 53.4%) whereas based on the ANSWER HDE Study the rate of complete occlusion is expected to be 58.8% with the PulseRider device. With Sponsor’s desire to seek superiority to a PG of 46.3% for the primary effectiveness endpoint and an expected attrition rate of 10%, one hundred sixty (160) subjects will provide 80% power for the primary safety endpoint and 85% power for the primary effectiveness endpoint.

10.3. Analyses to be Conducted

10.3.1. General Conventions

Standard descriptive summaries for continuous data include the number of observations with data, number of observations with missing data, mean, standard deviation, median, minimum, and maximum values. For categorical data, the count and percent will be provided. Percentages will be based on the number of subjects without missing data.

Analyses will take place using SAS statistical software version 9.4 or later in a server environment.

10.3.2. Disposition of Study Subjects

Subject disposition will be summarized in multiple ways:

- With a summary of the number of subjects enrolled and treated by site/investigator
- With a subject flow diagram which shows the number of enrolled, discontinued, lost to follow-up, withdrawn/early terminated, and completed subjects
- With a subject accounting table

10.3.3. Demographics, Baseline, and Procedural Characteristics

All demographic characteristics, procedural, and immediate post-operative details will be summarized using the mITT analysis set, including but not limited to: age, sex, medical history, smoking status, prior treatment, aneurysm location, neck and diameter size, pre and post procedural DAPT, length of procedure, and length of hospital stay.

10.3.4. Primary Endpoint Analyses

Primary Safety Endpoint

The primary safety endpoint analysis will be conducted on the mITT analysis set.

If a subject experienced a death due to neurological causes or a major ipsilateral stroke in downstream territory within a year post-procedure then subject will be deemed a failure on the endpoint. If a subject completed the 1 year follow up and did not experience any such event then subject will be deemed a success on the endpoint. If a subject did not complete the 1 year follow up and did not experience such event then the subject will be imputed with a multiple imputation method that will make use of the similarities between the subject's demographic, procedural, and aneurysm characteristics with those of the subjects with a non-missing endpoint (those who either experienced an event and those who completed the study without experiencing an event). The imputation method will also account for the length of time between the procedure and the last time the subject was seen. The longer that time period is, the less likely the subject will be imputed with an event.

Subjects for whom implantation of the PulseRider was attempted but not successful will be followed up to a year. Any safety events which occur due to attempted implant or from retreatment, and which meet the primary safety endpoint definition will count as failures in the analysis. If such a subject is lost to follow-up then subject will be imputed with data based on other subjects for whom the implantation was not successful but who were not lost to follow-up.

The multiple imputation method results in a large collection of imputed datasets. The proportion of primary endpoint events and its variance is computed for each dataset. Within and between imputation variances are then combined according to Rubin's method [Rubin 1996] in order to produce a single variance estimate for the proportion of events.

The endpoint will be considered successful if the upper bound of the 2-sided 95% normal approximation based confidence interval for the rate of events is less than a performance goal of 15%.

Primary Effectiveness Endpoint

The primary effectiveness endpoint analysis will be conducted on the PP analysis set.

Success on this endpoint is defined as complete aneurysm occlusion (Raymond I) without retreatment or significant parent artery stenosis (> 50% stenosis) at 1 year post-procedure. If the 1 year imaging is not available and if the subject did not experience a retreatment then the subject will be imputed using an imputation method that will make use of the subject's own past occlusion and stenosis evaluations if available and the similarities between the subject's demographic, procedural, and aneurysm characteristics with those of the subjects with a non-missing endpoint.

The multiple imputation method results in a large collection of imputed datasets. The proportion of complete aneurysm occlusion and its variance is computed for each dataset. Within and between imputation variances are then combined according to Rubin's method in order to produce a single variance estimate for the proportion of complete aneurysm occlusion.

The endpoint will be considered successful if the lower bound of the 2-sided 95% normal approximation based confidence interval for the rate is greater than a performance goal of 46.3%.

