3.2. Study Endpoints

3.2.1. Primary Endpoint - Safety

Composite of Neurological Death or Major Ipsilateral Stroke (in downstream territory) up to 1 year post-procedure:

Stroke is defined as rapidly developing clinical signs of focal (or global) disturbance of cerebral function lasting more than 24 hours with no apparent cause other than of vascular origin, including ischemic stroke and/or hemorrhagic stroke (i.e., intraparenchymal hemorrhage (IPH), subarachnoid hemorrhage (SAH), subdural hemorrhage (SDH), epidural hemorrhage (EDH)) [Hatano 1976].

Major Stroke is defined as stroke with symptoms persisting for more than 24 hours AND a sudden increase in the NIHSS of the subject by > 4 .

Minor Stroke is defined as stroke with symptoms persisting for more than 24 hours and a sudden increase in the NIHSS of the subject by 1-3.

TIA is defined as stroke symptoms resolving within ≤ 24 hours.

This endpoint will be adjudicated by the independent Clinical Events Committee (CEC).

[figure not shown]

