10.1.6. Analysis Datasets

Modified Intent to Treat Analysis Set

The mITT analysis set consists of all enrolled subjects in whom treatment with the PulseRider device is attempted as defined by advancement of any portion of the PulseRider device outside of the distal end of the microcatheter inside the subject. This includes subjects in which the PulseRider is not fully advanced outside of the microcatheter. It is possible that the PulseRider device may not reach the target aneurysm, and as a result the treating physician does not advance the device outside of the distal end of the microcatheter. In the rare event that this happens, the subject will not be considered part of the mITT population and will instead be followed for 30 days.

Per Protocol (PP) Analysis Set

The PP analysis set consists of all subjects who meet the following criteria:

- there are no major deviations from the protocol eligibility criteria or DAPT requirements
- the subject is successfully implanted with the PulseRider device

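### Section 10.3.4 scores primary safety in failed-implant subjects with causal wording that the endpoint lacks, and this can be read to leave out qualifying events

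*Combined protocol and SAP*

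**What the plan says.** Section 3.2.1 defines the primary safety endpoint as "Composite of Neurological Death or Major Ipsilateral Stroke (in downstream territory) up to 1 year post-procedure" and gives its adjudication to the independent Clinical Events Committee (CEC). The hypotheses in section 10.1.1 use the same composite. Neither place asks whether the event was related to the device, the procedure or a later treatment.

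Section 10.3.4 then sets the scoring rules.

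- **Analysis set.** "The primary safety endpoint analysis will be conducted on the mITT analysis set". Section 10.1.6 builds that set from attempted treatments and says of it: "This includes subjects in which the PulseRider is not fully advanced outside of the microcatheter". Failed implants therefore belong to it.
- **General failure rule.** A subject with a qualifying event "within a year post-procedure then subject will be deemed a failure on the endpoint". No cause is required.
- **General success rule.** This rule, with its last word left off here, reads: "If a subject completed the 1 year follow up and did not experience any such event then subject will be deemed a success on the".
- **Failed-implant rule.** A further paragraph covers subjects in whom implantation was attempted without success. They are followed for up to a year, and "Any safety events which occur due to attempted implant or from retreatment, and which meet the primary safety endpoint definition will count as failures".

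**The concern.** The failed-implant sentence sets two requirements joined by "and": the event must arise from the attempt or from retreatment, and it must meet the endpoint definition. The general rule, in the paragraph just before, has only the second. The general rule already covers these subjects, so the causal clause does no work unless it narrows what counts. Someone programming the endpoint from 10.3.4 could reasonably apply it that way.

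The events exposed are plausible ones. Stroke in section 3.2.1 includes subarachnoid hemorrhage. A rupture months later of an aneurysm left untreated after a failed attempt is hard to attribute to the attempt. Section 7.11 describes retreatment for subjects who have received the device, so a stroke from the alternative treatment given after a failed implant may fit neither causal category cleanly. The causality grading in section 8.2.2 covers device and study procedure but not retreatment, and the plan sets no cut-off for attribution in this endpoint.

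Any omission would go one way, lowering the observed event rate, and would affect only subjects in whom the device failed. It would also make the comparison uneven, because section 10.1.1 describes no relatedness filter for the literature events behind the 15% goal. A failed-implant subject lost to follow-up is imputed from other failed-implant subjects, so an omitted event would lower their imputed rate as well.

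**Working it through.** **Inputs.** 160 subjects, 10% attrition, anticipated safety rate 7%, performance goal 15% (section 10.2). Success requires the upper limit of a two-sided 95% normal-approximation interval to be below 15% (sections 10.1.1 and 10.3.4). Technical success has a goal of 79% and needs at least 85% observed with 160 subjects (section 10.1.2). Earlier implant success was 34/34 (section 1.3.2). The share of failed-implant events that would be judged unrelated is not in the documents. It is assumed here at 25% to 100%.

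**1. The plan's own figures.** With n = 160 × 0.9 = 144, a one-sample test using the null variance and a continuity correction gives power

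Φ[(0.08 − 1/288 − 1.96·√(0.15·0.85/144)) / √(0.07·0.93/144)] = 80.4%,

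which reproduces the stated 80%. The 85% for technical success also reproduces: 136/160 gives a lower limit of 0.850 − 1.96·√(0.85·0.15/160) = 79.5%, above 79%, while 135/160 gives 0.844 − 1.96·√(0.844·0.156/160) = 78.7%, below it. So 24 failed implants is the most that still passes that secondary test.

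**2. Where the safety decision turns.** Upper limit = x/n + 1.96·√[(x/n)(1 − x/n)/n], taking complete data.

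| n | passes | upper limit | fails | upper limit |
|---|---|---|---|---|
| 160 | 16 | 14.6% | 17 | 15.4% |
| 144 | 14 | 14.6% | 15 | 15.4% |

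One event moves the rate by 1/160 = 0.6 or 1/144 = 0.7 percentage points. Multiple imputation would add between-imputation variance, so the exact cut may shift.

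**3. Events at stake on the restrictive reading.** Expected omitted events = 160 × failed share × 0.07 × share judged unrelated, taking the 7% rate to apply equally to failed implants.

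| failed share | failed implants | omitted events (25% to 100% unrelated) |
|---|---|---|
| 0% | 0 | 0 |
| 5% | 8 | 0.1 to 0.6 |
| 15% | 24 | 0.4 to 1.7 |
| 21% | 33.6 | 0.6 to 2.4 |

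**4. Effect on the error rate.** Suppose the true rate is exactly 15% and n = 160. The chance of 16 or fewer events, which is the exact one-sided error of the rule, is 4.3% with full counting. If a failed share f has a fraction u of its events dropped, the counted rate is 0.15 × (1 − f·u).

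- f = 5%, u = 50%: counted rate 14.6%, error 5.6%.
- f = 15%, u = 50%: counted rate 13.9%, error 9.2%.
- f = 21%, u = 100%: counted rate 11.9%, error 28%. This is an extreme bound, not an expectation.

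**5. Classification on the restrictive reading.** Take a failed-implant subject who completes 1 year after a qualifying stroke that nobody attributes to the attempt or to retreatment. The failed-implant sentence does not make this subject a failure. The general success rule does not apply either, because it requires that no such event occurred. The outcome is not missing, so imputation does not apply. The subject has no defined score.

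**The case against.** The strongest reply is that the sentence includes events and excludes none. It nowhere says that only these events count. It can be read as reassurance that a subject who leaves without the device still contributes events, including those from a later alternative treatment. The general rule applies to the whole mITT set and already makes any qualifying event a failure. To say that some events count does not contradict a rule that all of them do. Adjudication rests with the CEC, and nothing in the endpoint makes relatedness part of its task.

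Most of this stands. A reader might infer that the plan definitely excludes unrelated events in failed-implant subjects, or that it scores such subjects as safety successes. The documents support neither. The first is one possible reading of loose wording, and the second contradicts the general success rule.

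The size must also be kept in proportion. The 85% technical success rate is a threshold for a secondary test, not a floor for the study, since study success depends on the two primary endpoints alone. The 1.7 events are all those expected among 24 failed implants, so they are a ceiling for that scenario. At the planned 7%, about 160 × 0.07 = 11.2 events are expected, well below the cut of 16. Any threshold rule can turn on one event.

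The reply does not explain why a causal clause is there at all, or how an analyst should score an event that fails it.

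**Conclusion.** The point holds as a conflict of wording in the primary safety analysis. Two neighbouring paragraphs of 10.3.4 give different scoring tests for the same subjects, and one carries a causal condition found nowhere else in the endpoint. It should not be stated as a settled exclusion of events.

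The likely effect is small, and close to zero if technical success is near 34/34. In the illustration with 15% failed implants it is at most about 1.7 events. That rests on three assumptions: the failed share, a 7% event rate in failed implants, and the share judged unrelated. It matters because the ambiguity sits in the numerator of a primary endpoint, can act only in the device's favour, and could decide a result near the cut. It is better settled before the data are seen.

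**What to change.** In the failed-implant paragraph of section 10.3.4, delete the clause that ties the event to the attempted implant or to retreatment. State in its place that every CEC-adjudicated neurological death or major ipsilateral stroke within the 1-year window is a failure for every mITT subject, whatever the implant result and whatever the attribution. Carry the same rule into the endpoint derivation in the separate SAP that section 10 announces.

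The cost is one sentence. The observed safety rate may come out slightly higher than under the restrictive reading. Sample size and the stated 80% power do not change, because the 7% and 15% inputs are given for the endpoint without a causal condition.

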- The percentage of subjects with mRS 0-2 at 1 year, 3 years and 5 years

Additional Endpoints:

- The percentage of target aneurysm rupture up to 1 year, 3 years and 5 years
- No migration (defined as ≤ 2 mm) of the device at 1 year, 3 years and 5 years

Sample Size Justification

A meta-analysis was executed to determine the Performance Goal (PG) for the primary safety endpoint of a clinical study of the PulseRider®. Based on this meta-analysis, a rate of 9.9% rounded to 10% (95% CI: 5.9% - 16.1%) for death due to neurological causes or major ipsilateral stroke was calculated. A 5% margin of indifference for the primary safety endpoint is proposed, resulting in a PG of 15% for this endpoint. Based on the 1 year results of the ANSWER HDE Study, the anticipated rate for the primary safety endpoint is 7%. Results from a recently published meta-analysis [Fiorella 2017] indicate that the rate of complete occlusion at 1 year of wide-neck bifurcated aneurysms treated with conventional therapies is 46.3% (95% CI: 39.2% - 53.4%) whereas the ANSWER HDE Study described above reports the rate of complete occlusion is 58.8% with the PulseRider® device. With Sponsor's desire to seek strict superiority to a PG of 46.3% for the primary effectiveness endpoint and an expected attrition rate of 10%, one hundred sixty (160) subjects will provide 80% power for the primary safety endpoint and 85% power for the primary effectiveness endpoint.

Statistical Analysis

The primary safety endpoint will be evaluated on all subjects for whom implantation of the PulseRider® device was attempted. Subjects with a missing endpoint will be imputed with a multiple imputation method that will make use of the similarities between the subject's demographic, procedural, and aneurysm characteristics with those of the subjects with a non-missing endpoint. The endpoint will be considered successful if the upper bound of the two-sided 95% confidence interval for its rate is less than a performance goal of 15%.

The primary effectiveness endpoint will be evaluated on all subjects for whom implantation of the PulseRider® device was successful. Subjects with a missing endpoint will be imputed using a multiple imputation method that will make use of the subject's own past

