Alternative hypothesis H_A : $p_{\text{Major Stroke/Death}} < 15\%$

Where $p_{\text{Major Stroke/Death}}$ is the rate of Composite of Neurological Death or Major Ipsilateral Stroke (in downstream territory) up to 1 year post-procedure.

Decision Criterion: The decision will be made to reject the null hypotheses and conclude the alternative hypothesis if the upper bound of a two-sided 95% normal approximation based confidence interval is < 15%.

Primary Effectiveness Endpoint Hypotheses:

Null hypothesis H_0 : $p_{\text{CompleteOcclusion}} \leq 46.34\%$

Alternative hypothesis H_A : $p_{\text{CompleteOcclusion}} > 46.3\%$

Where $p_{\text{CompleteOcclusion}}$ is the rate of complete aneurysm occlusion without significant parent artery stenosis ($> 50\%$ stenosis) or prior retreatment at 1 year post-procedure.

Decision Criterion: The decision will be made to reject the null hypotheses and conclude the alternative hypothesis if the lower bound of a two-sided 95% normal approximation based confidence interval is $> 46.3\%$.

Study Success:

The study will be deemed to be a success if the primary safety and effectiveness endpoint null hypotheses are both rejected.

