10.1.2. Secondary Endpoints

- Technical Success is defined as successful implantation of device— physician able to access target aneurysm, deploy PulseRider device at the neck of aneurysm and device was detached successfully. This endpoint will be reported by the investigator. The following hypothesis test of this endpoint will be performed if the primary safety and effectiveness endpoint null hypotheses are both rejected:
 - Null hypothesis H_0 : $p_{\text{TechnicalSuccess}} \leq \text{PG of } 79\%$
 - Alternative hypothesis H_A : $p_{\text{TechnicalSuccess}} > \text{PG of } 79\%$
 - Where $p_{\text{TechnicalSuccess}}$ is the rate of technical success
 - Decision Criterion: The decision will be made to reject the null hypotheses and conclude the alternative hypothesis if the lower bound of a two-sided 95% normal approximation based confidence interval is $> \text{PG of } 79\%$. With 160 subjects, a rate for technical success of at least 85% is required to demonstrate success on this endpoint.
- Ability to retain embolic coils within aneurysm immediately post-procedure (as evaluated by the core lab)
- Complete aneurysm occlusion at 3 years and 5 years. Complete aneurysm occlusion is defined as Raymond I. Aneurysm occlusion grading will be evaluated by the independent core laboratory.
- Adequate aneurysm occlusion (defined as Raymond I and II combined) at 1 year, 3 years and at 5 years. Aneurysm occlusion grading will be evaluated by the independent core laboratory.
- The percentage of target aneurysms that are retreated through 1 year, 3 years and 5 years. Retreatment will be reported by the investigator.

- The percentage of subjects with significant stenosis defined as $> 50\%$ at implant site at 1 year, 3 years and 5 years. This endpoint will be evaluated by the independent core laboratory
- The percentage of subjects with mRS 0 – 2 at 1 year, 3 years and 5 years

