10.1.5. Levels of Significance

A 2-sided alpha of 0.05 will be used for statistical testing and confidence intervals unless otherwise noted. There will be no adjustment of significance levels or p-values for testing multiple hypotheses. Both primary endpoints must be met for study success and the secondary effectiveness endpoint of technical success will only be tested if the primary endpoints are met.

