10.3.10. Sensitivity Analyses

As a sensitivity analysis, the primary safety and effectiveness endpoints will be analyzed as described in section 10.5.4 but without imputing missing endpoint data using the Clopper-Pearson method.

Other sensitivity analyses will analyze the primary endpoints as follows:

- Consider all missing endpoints as successes,
- Consider all missing endpoints as failures,
- A Tipping point analysis which attempts to answer how many subjects with missing primary endpoint data need to change to either successes or failures for success on the endpoint to no longer hold.

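### The primary safety rule uses a Wald upper bound, so with complete data its exact one-sided false-success rate at a true 15% is 4.3%, against a nominal 2.5%

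*Combined protocol and SAP*

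**What the plan says.** Section 10.1.1 rejects the safety null hypothesis "if the upper bound of a two-sided 95% normal approximation based confidence interval is < 15" percent. Section 10.3.4 repeats the rule in these words: "upper bound of the 2-sided 95% normal approximation based confidence interval for the rate of events is less than a performance goal of 15" percent. For the variance, Section 10.3.4 says: "The proportion of primary endpoint events and its variance is computed for each dataset". The results are then pooled by Rubin's method, so with no missing outcomes the interval is the plain Wald interval.

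Section 10.1.5 sets the level: "A 2-sided alpha of 0.05 will be used for statistical testing and confidence intervals unless otherwise noted". Only the upper bound matters for safety, so the false-success probability should be 2.5%.

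The Protocol Summary gives the rule as "upper bound of the two-sided 95% confidence interval for its rate is less than a performance goal of 15" percent and names no interval method. An exact interval appears only in Section 10.3.10, which repeats the primary analyses on observed data, "but without imputing missing endpoint data using the Clopper-Pearson method". Nothing there lets that result govern the gate.

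**The concern.** The interval asks whether the observed rate lies about two standard errors below 15%, but it uses the standard error at the observed rate. To pass, that rate must be about 10% or lower, where the binomial variance is well below its value at 15%. The upper bound is therefore too low, and the rule passes results that a test at the stated level would not.

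Safety is one of two gates that must both be met for study success, in a single-arm study meant to support a pre-market approval application. There is no control arm to offset a lenient rule. At the pass limit the study could also declare safety success while its own Clopper-Pearson analysis gives an upper bound above 15%.

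**Working it through.** **Inputs.** Performance goal 15%, anticipated rate 7%, 160 enrolled, 10% attrition (160 × 0.9 = 144), stated safety power 80% (Section 10.2). Two-sided 0.05 (Section 10.1.5).

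**The plan's own figures.**
- *Technical success.* Section 10.1.2 says: "With 160 subjects, a rate for technical success of at least 85% is required to demonstrate success on this endpoint". The Wald lower bound first exceeds 79% at 136/160 = 85.0%; a Wilson bound needs 137/160 = 85.6%. The plan therefore means Wald.
- *Safety power.* The stated 80% reproduces at n = 144 with a continuity-corrected z-test using the null variance: [0.15 − 0.07 − 1/288 − 1.96·√(0.15·0.85/144)] / √(0.07·0.93/144) = 0.856, giving 80.4%. That is not the planned rule, whose exact power is 92.0%.

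**Pass limit.** Find the largest x with x/n + 1.96·√[(x/n)(1 − x/n)/n] < 0.15.
- n = 160: 16 events gives 0.10 + 1.96·√(0.10·0.90/160) = 14.65% (pass); 17 gives 15.40% (fail).
- n = 144: 14 events gives 14.56% (pass); 15 gives 15.41% (fail).

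**Exact error at a true 15%.**
- P(X ≤ 16 | 160, 0.15) = 4.31%.
- P(X ≤ 14 | 144, 0.15) = 4.31%.

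The ratio to nominal is 4.31/2.5 = 1.7. At a true 16% the false-pass rate is 2.0% (n = 160) and 2.1% (n = 144).

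**Mechanism.** At 16/160 the observed-rate standard error is √(0.10·0.90/160) = 0.0237, so 15% is 0.05/0.0237 = 2.11 standard errors away. With the standard error under the null, √(0.15·0.85/160) = 0.0282, it is only 0.05/0.0282 = 1.77.

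**Comparison of bounds, complete data.**

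| n | Bound | Passes at | Error at 15% | Power at 7% |
|---|---|---|---|---|
| 144 | Wald | ≤ 14 | 4.31% | 92.0% |
| 144 | Wilson | ≤ 13 | 2.40% | 86.7% |
| 160 | Wald | ≤ 16 | 4.31% | 94.3% |
| 160 | Wilson | ≤ 15 | 2.48% | 90.4% |

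Clopper-Pearson gives the same limits as Wilson at these two sizes. Its upper bound is 15.8% at 14/144 and 15.7% at 16/160.

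**Other sizes, same range for both methods (n = 130 to 160).** Wald error runs from 3.3% (n = 156) to 5.7% (n = 132) and exceeds 2.5% at every size. Wilson error runs from 1.4% to 2.7% and exceeds 2.5% only at n = 135, 143, 151 and 159. Wilson power at 7% is below 80% only at n = 131 to 134 (77.1% to 79.3%). Over n = 144 to 160 it is 83.3% to 90.8%.

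**Contrast with effectiveness.** A Wald lower bound above 46.3% needs 79/144 or 87/160, with exact error 2.42% and 2.46%. The interval works there because the rate is near one half.

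**Imputed data (assumption-based).** Section 10.3.4 describes the imputation model only in general terms, so the realised error cannot be computed. Simulations assumed n = 160, 5% to 15% missing completely at random, imputation from the observed rate and 50 imputations. In repeated sets of 20,000 runs the Wald error was about 4.0% to 4.4%. The imputation-compatible Wilson bound (formula under the fix) had error 1.8% to 2.2% and power 81% to 87%.

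**The case against.** The strongest reply is that the practical effect is small. The Wald rule has 2.5% error at a true rate of about 15.7% to 15.8%, so it acts like a goal 0.7 to 0.8 points higher. The 15% goal is itself a 9.9% estimate (95% CI 5.9% to 16.1%), rounded and then given a chosen 5-point margin. At n = 160 the two rules differ only at exactly 16 events, which has probability 1.8% at a true 15% and 3.9% at a true 7%. All of this is correct, and it is why the defect is not fatal. It does not justify a rule that misses its own stated level when a standard alternative meets it.

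The 4.3% belongs to the safety gate, not to study success. If effectiveness is truly 58.8% and the endpoints are independent (an assumption), false study success at n = 160 is about 0.043 × 0.888 = 3.8%. That is still above 2.5%.

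The analysis set is the modified intent-to-treat set with missing outcomes imputed, so the relevant n should be close to 160. The 5.7% at n = 132 should not be the headline, and the sizes where Wilson power falls below 80% are equally unlikely. The figures at 160 and 144 carry the point.

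The simulations are illustrative: the plan's model uses covariates, time last seen and separate donors for failed implants. Certainty attaches to the complete-data result.

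**Conclusion.** The rule is wrong as written. With complete binomial data its one-sided error at a true 15% is 4.3% at both n = 144 and n = 160, about 1.7 times the 2.5% implied by Section 10.1.5, and it exceeds 2.5% at every n from 130 to 160. The planned Clopper-Pearson analysis exposes a borderline result but does not control the gate. Power is not the problem, and the effectiveness rule is sound. The error under the plan's multiple imputation is not determined by the documents; under the simple model assumed here, imputation does not remove the inflation. This should be fixed, but it does not invalidate the design.

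**What to change.** In Sections 10.1.1 and 10.3.4, replace the normal-approximation bound for safety with an imputation-compatible Wilson upper bound, and write out the formula:

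- Q = mean imputed proportion; U and B = within- and between-imputation variances; M = number of imputations.
- r = (1 + 1/M)·B/U; t = 97.5% quantile of Student's t on Rubin's degrees of freedom; k = t²(1 + r)/n.
- Upper bound = [2Q + k + √((2Q + k)² − 4Q²(1 + k))] / [2(1 + k)].

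This is the larger root p of (Q − p)² = k·p(1 − p). With no missing data, r = 0 and t = 1.96, so it becomes the ordinary Wilson bound: 14.9% at 15/160 and 15.6% at 16/160.

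Name the same method in the Protocol Summary's safety rule. Keep Clopper-Pearson for the observed-data sensitivity analysis, and leave the effectiveness rule unchanged. A Wilson lower bound for technical success is optional: the Wald error there is 3.5% at n = 160, the required count would move from 136 to 137 (error 2.1%), and the 85% in Section 10.1.2 would become 85.6%.

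**Cost.** Wording in two sections, a phrase in the summary and a formula in the SAP, with no change to sample size or data collection. The pass limit is one event stricter at n = 144 and 160, and two stricter at some sizes between (for example n = 148 to 150 and 157 to 158). Complete-data safety power at 7% falls from 94.3% to 90.4% at n = 160 and from 92.0% to 86.7% at n = 144. In the simulation with 10% missing it falls from about 92% to 84%. If the endpoints are independent, complete-data power for study success at n = 160 goes from 0.943 × 0.888 = 83.7% to 0.904 × 0.888 = 80.3%.
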